## 8.3 ADVERSE EVENTS AND SERIOUS ADVERSE EVENTS

### 8.3.1 DEFINITION OF ADVERSE EVENTS

This protocol uses the definition of adverse event from 21 CFR 312.32 (a): any untoward medical occurrence associated with the use of an intervention in humans, ***whether or not considered intervention-related.***

### 8.3.2 DEFINITION OF SERIOUS ADVERSE EVENTS

For this study a serious adverse event includes, as outlined at: <https://www.hhs.gov/ohrp/regulations-and-policy/guidance/reviewing-unanticipated-problems/index.html>:

1. results in death;
2. is life-threatening (places the subject at immediate risk of death from the event as it occurred);
3. results in inpatient hospitalization or prolongation of existing hospitalization;
4. results in a persistent or significant disability/incapacity;
5. results in a congenital anomaly/birth defect; or
6. based upon appropriate medical judgment, may jeopardize the subject's health and may require medical or surgical intervention to prevent one of the other outcomes listed in this definition (examples of such events include allergic bronchospasm requiring intensive treatment in the emergency room or at home, blood dyscrasias or convulsions that do not result in inpatient hospitalization, or the development of drug dependency or drug abuse)

---

### 8.3.3 CLASSIFICATION OF AN ADVERSE EVENT

---

#### 8.3.3.1 SEVERITY OF EVENT

For adverse events (AEs) not included in the protocol defined grading system, the following guidelines will be used to describe severity.

- **Mild** – Events require minimal or no treatment and do not interfere with the participant's daily activities.
- **Moderate** – Events result in a low level of inconvenience or concern with the therapeutic measures. Moderate events may cause some interference with functioning.
- **Severe** – Events interrupt a participant's usual daily activity and may require systemic drug therapy or other treatment. Severe events are usually potentially life-threatening or incapacitating. Of note, the term "severe" does not necessarily equate to "serious".

---

#### 8.3.3.2 RELATIONSHIP TO STUDY INTERVENTION/EXPERIMENTAL MANIPULATION

All adverse events (AEs) will have their relationship to study procedures, including the intervention, assessed by an appropriately-trained clinician based on temporal relationship and his/her clinical judgment. The degree of certainty about causality will be graded using the categories below.

- **Definitely Related** – There is clear evidence to suggest a causal relationship, and other possible contributing factors can be ruled out. The clinical event, including an abnormal laboratory test result, occurs in a plausible time relationship to study procedures administration and cannot be explained by concurrent disease or other drugs or chemicals. The response to withdrawal of the study procedures should be clinically plausible. The event must be pharmacologically or phenomenologically definitive.
- **Probably Related** – There is evidence to suggest a causal relationship, and the influence of other factors is unlikely. The clinical event, including an abnormal laboratory test result, occurs within a

reasonable time after administration of the study procedures, is unlikely to be attributed to concurrent disease or other drugs or chemicals, and follows a clinically reasonable response on withdrawal.

- **Potentially Related** – There is some evidence to suggest a causal relationship (e.g., the event occurred within a reasonable time after administration of study procedures). However, other factors may have contributed to the event (e.g., the participant's clinical condition, other concomitant events). Although an AE may rate only as "possibly related" soon after discovery, it can be flagged as requiring more information and later be upgraded to "probably related" or "definitely related", as appropriate.
- **Unlikely to be related** – A clinical event, including an abnormal laboratory test result, whose temporal relationship to study procedures administration makes a causal relationship improbable (e.g., the event did not occur within a reasonable time after administration of the study procedures) and in which other drugs or chemicals or underlying disease provides plausible explanations (e.g., the participant's clinical condition, other concomitant treatments).
- **Not Related** – The AE is completely independent of study procedures administration, and/or evidence exists that the event is definitely related to another etiology. There must be an alternative, definitive etiology documented by the clinician.

---

#### 8.3.4 TIME PERIOD AND FREQUENCY FOR EVENT ASSESSMENT AND FOLLOW-UP

Solicited potential adverse events will occur at each visit and follow-up measurement visit. They include the following and we will ask if evaluation for these events included emergency room visit or overnight hospital stay.

- Acute myocardial infarction
- Angina pectoris
- Stroke
  - Thrombotic
  - Hemorrhagic
- TIA
- Heart failure
- Coronary bypass surgery
- Cancer
  - Type of cancer
- Broken bone
  - Type of fracture
- Light headedness or dizziness
- Pneumonia
- Other infection
  - UTI
  - Other
- Hypoglycemia
  - Other

Unsolicited adverse events (AE) or serious adverse events (SAE) may come to the attention of study staff during counseling visits, phone calls, or via other channels of communications. They will be categorized as above and entered into the appropriate follow-up questionnaire at the time of occurrence.

Information to be collected about AEs and SAEs includes event description, time of onset, study clinician's assessment of severity, relationship to study procedures (assessed only by those with the training and authority to make a diagnosis), and time of resolution/stabilization of the event. All AEs occurring while on study will be documented appropriately regardless of relationship. All AEs will be followed to adequate resolution.

Any medical or psychiatric condition that is present at the time that the participant is screened will be considered as baseline and not reported as an AE. However, if the study participant's condition deteriorates at any time during the study, it will be recorded as an AE.

Changes in the severity of an AE will be documented to allow an assessment of the duration of the event at each level of severity to be performed. Documentation of onset and duration of each episode will be maintained for AEs characterized as intermittent.

Study staff will record events with start dates occurring any time after informed consent is obtained until the last day of study participation.

---

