### 2.3 RISK/BENEFIT ASSESSMENT

#### 2.3.1 KNOWN POTENTIAL RISKS

The possible risks and discomforts from being in this study are few and are listed below.

- We do not think there is risk from the dietary advice given as part of the study
- Those who increase their level of physical activity may experience minor muscle pain, but this type of activity rarely causes serious health problems such as chest pain or asthma.
- In all studies, there is a very slight chance of loss of privacy (that is, others may see your study information). As stated below, we will do all we can to make sure this does not happen.

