#### 9.4.4 SAFETY ANALYSES

Prior to analysis, any data-captured adverse events will be coded by the principal investigators. Each type of event (by seriousness, severity, relationship to study) will be descriptively summarized in frequency tables by group (including only a single occurrence of any distinct type of event for any participant). Number of CVD events, ER visits, and hospitalizations will also be descriptively summarized by group. No inferential statistics (p-values or confidence intervals) are planned for comparing safety data between groups.

---

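### The solicited adverse-event list asks about neither muscle pain nor asthma, so the descriptive safety tables can under-count the mild event the intervention most plausibly causes

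*Combined protocol and SAP*

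**What the plan says.** Section 2.3.1 (Known Potential Risks) says that people who become more active "may experience minor muscle pain, but this type of activity rarely causes serious health problems such as chest pain or asthma". It also says that "there is a very slight chance of loss of privacy".

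Section 8.3.4 sets the timing of active questioning: "Solicited potential adverse events will occur at each visit and follow-up measurement visit". It introduces the list with "They include the following and we will ask if evaluation for these events included emergency room visit or overnight hospital stay". The items are myocardial infarction, angina, stroke, TIA, heart failure, bypass surgery, cancer, fracture, dizziness, pneumonia, other infection and hypoglycemia. In the available text, lines reading Other appear only beneath infection and hypoglycemia.

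The same section describes a second route: "Unsolicited adverse events (AE) or serious adverse events (SAE) may come to the attention of study staff during counseling visits, phone calls", or by other channels. Such events are to be categorized and entered when they occur, and every adverse event on study is to be documented whatever its cause.

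Section 9.4.4 takes all captured adverse events, counts each distinct type once per participant, and says that they "will be descriptively summarized in frequency tables by group". It plans no p-values or confidence intervals.

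**The concern.** The risk section and the data-collection section do not match. Muscle pain is the only physical effect that the protocol presents as something participants may experience, and staff are not instructed to ask about it. Asthma, named as rare, is not asked about either. The list does cover major cardiovascular events, cancer and pneumonia.

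Active questioning and waiting for volunteered reports do not capture mild symptoms equally well. A participant with sore muscles after starting to exercise may see no reason to mention it. If the form does not prompt for it, a low count in the safety table cannot be told apart from a symptom that nobody asked about. What is at stake is how complete a descriptive table in a small pilot will be, and whether its muscle-pain row can be interpreted.

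**Working it through.** The plan gives no expected adverse-event rate and no power or error rate for safety, so there is no figure to reproduce. The check compares the sections and then gives an illustration on stated assumptions.

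**Step 1: named physical risks against the solicited list**

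| Physical risk in 2.3.1 | How 2.3.1 describes it | Item in 8.3.4 |
|---|---|---|
| Muscle pain | may occur, minor | none (fracture is the only musculoskeletal item) |
| Chest pain | rare | angina, in part |
| Asthma | rare | none |

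Two of the three have no prompt. Only muscle pain is described as something to be anticipated.

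**Step 2: how an unprompted event reaches the tables**

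- Section 8.3.1 defines an adverse event as an untoward medical occurrence, whether or not related to the intervention. Muscle pain and asthma both qualify.
- Under 8.3.4 they can be recorded as unsolicited events, but only if they come to the notice of staff.
- Section 9.4.4 tabulates what has been captured. An event that was neither asked about nor volunteered cannot appear.

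Under-counting is therefore possible. It is not certain, because the unsolicited route exists and feeds the same tables.

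**Step 3: whether the loss would differ by arm**

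Section 6.1.1 gives all dyads the same 7 in-person core sessions, which include the physical activity content. The 2 skills sessions are led by a counselor in either mode. Planned staff contacts are 7 + 2 = 9 in each arm. Section 1.3 has a single visit schedule for both arms. Nothing here points to a difference between arms in the capture of muscle pain.

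**Step 4: possible size, on assumptions**

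Inputs: 20 participants randomized 1:1 (Sections 4.1 and 9.2), so n = 10 per arm. Assumed, not in the documents: muscle-pain incidence p from 20% to 50%, and the share volunteered without a prompt c from 25% to 100%.

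- Affected per arm = n × p: 10 × 0.20 = 2, up to 10 × 0.50 = 5.
- Recorded per arm = n × p × c: 2 × 0.25 = 0.5 at the lowest, up to 5 × 1.00 = 5.
- Missed per arm = n × p × (1 − c): 0 when c = 100%, up to 5 × 0.75 = 3.75.

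The range starts at zero. At its upper end, most of the affected participants would be absent from the table.

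**The case against.** The strongest reply is that the plan already captures these events. The list is introduced as what the solicited events include, so it may not be exhaustive. All adverse events are to be documented, and 9.4.4 is not limited to checklist items. The final Other line, which sits oddly under hypoglycemia, may be a general category displaced when the text was read from PDF. The trial is a minimal-risk pilot aimed at feasibility and acceptability, and its safety summary is descriptive. All of this stands, and it rules out saying that the tables will under-count. It does not supply a prompt for muscle pain, and documenting every event depends on staff first hearing of it.

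A reader might infer three stronger points, which the documents do not support.

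- **Ascertainment differs between arms.** Face-to-face sessions number 7 + 2 = 9 in person and 7 online, and (9 − 7)/9 is about 22%. This is not a measure of bias. The online sessions are live contacts with a counselor, unsolicited reports need not be made face to face, and solicitation follows one schedule.
- **Loss of privacy belongs on the list.** Section 8.3.1 limits adverse events to medical occurrences, and a privacy breach is not one. The unanticipated-problem route in 8.4.1 covers social harm but requires the event to be unexpected, and 2.3.1 already names privacy loss. That may justify a separate item, but it does not make privacy loss an adverse event. Family conflict is not among the risks in 2.3.1 at all.
- **Asthma is an expected harm.** Section 2.3.1 mentions it only to say that it is rare.

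**Conclusion.** The point holds as a modest, inexpensive improvement. Muscle pain, the physical effect that 2.3.1 says may follow increased activity, and asthma, a rare one, are left to unsolicited reporting. The descriptive tables in 9.4.4 can therefore under-count the mild event most plausibly caused by the intervention.

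The size cannot be fixed from the documents. The range of 0 to 3.75 participants missed per arm rests entirely on the assumed incidence and capture rates and on 10 participants per arm. Any shortfall would be expected to lower the counts similarly in both arms. No between-arm bias is shown, and no planned inference is affected. The conclusion also assumes that the questionnaire in use follows the printed list. If it already carries a general open question about other events, the gap is smaller, though muscle pain would still have no specific prompt.

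**What to change.** Add three items to the solicited list in 8.3.4, asked in the same words and at the same visits in both arms:

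1. muscle pain or activity-related injury;
2. asthma or breathing difficulty with activity;
3. any other event since the last visit, as a general item standing apart from the infection and hypoglycemia lines.

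Tabulate them by group under 9.4.4 with the other events, marking which types were solicited, so that a zero can be read as asked and absent. If privacy concerns are of interest, record them as a separate item outside the adverse-event list.

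While editing, check the adverse-event row of the schedule in Section 1.3 against 8.3.4. As the table reads in the available text, Visits 1 and 2 carry no mark, whereas 8.3.4 says each visit. The table may have been damaged when read from PDF.

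The cost is three questions on a form already in use. The small downside is a higher count of mild events.

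### Emergency room visits and hospital stays are actively asked about only for the solicited events in 8.3.4, while 9.4.4 counts them without that limit, so the counts may be incomplete.

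*Combined protocol and SAP*

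**What the plan says.** Section 8.3.4 provides two routes by which events reach the record.

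- **Solicited events.** These are asked about at each visit and at follow-up measurement. The sentence that introduces the list says that the events include those that follow, and adds: "we will ask if evaluation for these events included emergency room visit or overnight hospital stay". The list covers several cardiovascular diagnoses, cancer, fracture, light-headedness, pneumonia, other infection and hypoglycemia. As printed, one Other line falls under infection and one under hypoglycemia.
- **Unsolicited events.** These "may come to the attention of study staff during counseling visits, phone calls, or via other channels of communications". The section continues: "They will be categorized as above and entered into the appropriate follow-up questionnaire at the time of occurrence". It also states: "All AEs occurring while on study will be documented appropriately regardless of relationship".

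On content, the same section says: "Information to be collected about AEs and SAEs includes event description, time of onset", followed by severity, relatedness and resolution. Emergency or hospital use is not named among these items.

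Section 8.3.2 treats an event as serious if, among other criteria, it "results in inpatient hospitalization or prolongation of existing hospitalization". Section 9.4.4 plans the output: "Number of CVD events, ER visits, and hospitalizations will also be descriptively summarized by group". It plans no p-values or confidence intervals for safety comparisons.

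**The concern.** The question that would populate the ER and hospitalization rows is narrower than the rows themselves, and narrower than the hospitalization criterion for an SAE. A participant seen in an emergency room or admitted for something off the list is never directly asked about it. A row labelled as all ER visits, or all hospitalizations, would then hold prompted reports for listed causes and volunteered reports for the rest.

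What is at stake is the accuracy of a small descriptive table and the completeness of SAE capture. Descriptive summaries are the only safety analysis planned. With the sample of 20 given in 9.2, one missed stay could decide whether a row reads 0 or 1.

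**Working it through.** The plan states no figure for this point, so there is none to reproduce. The check compares sections.

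**Scope of each element**

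- 8.3.4, active question: emergency or overnight care in connection with the solicited events.
- 8.3.4, unsolicited route: any AE or SAE that staff learn of, with no prompt and no named item for emergency or hospital use.
- 8.3.2: any adverse event resulting in inpatient hospitalization, with no limit by diagnosis.
- 9.4.4: ER visits and hospitalizations by group, with no limit by diagnosis.

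The last two are wider than the first. The second can bridge the difference only to the extent that participants volunteer the information and staff record where care was given.

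**Following an off-list ER visit.** Section 2.3.1 mentions muscle pain, chest pain and asthma in connection with physical activity. Asthma and muscle pain are not on the 8.3.4 list, and chest pain is reached only if it is identified as angina or infarction. Suppose a participant goes to an emergency room with asthma. The active question does not reach it. If the participant mentions it, staff record an AE, but no item is named that would carry the visit into the ER row of 9.4.4. Categorizing it in the same way as solicited events might supply one, but the text does not say so.

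**Following an off-list admission.** Section 7.2 anticipates nonmalignant gastrointestinal and rheumatologic disease as possible reasons for withdrawal, and neither is on the list. An admission for a new gastrointestinal illness would meet the 8.3.2 criterion, but its capture again depends on the participant raising it. Section 8.3.7 confirms that participants are the source of event reports. No record review to find events is described, 10.1.6 relies on self-assessment by the study team, and 10.1.7 marks clinical monitoring as not applicable. No later step is described that would recover a missed stay.

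**What can be said about size.** Let s be the share of ER visits or stays with off-list causes, and c the share of those picked up through the unsolicited route. The fraction missed is s × (1 − c). The documents give neither quantity. With values assumed purely for illustration:

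- s = 0.25, c = 0.8: 0.25 × 0.2 = 5%
- s = 0.5, c = 0.5: 0.5 × 0.5 = 25%
- s = 0.75, c = 0.2: 0.75 × 0.8 = 60%
- c = 1, any s: 0%

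The range runs from nothing to more than half, so the formula shows what the shortfall depends on and does not estimate it.

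**The case against.** The strongest reply is that the list is not closed. It is introduced by a word that does not claim completeness and it has Other lines. The last Other line sits oddly beneath hypoglycemia and may be a general catch-all whose indentation was lost when the PDF was read. The questionnaire itself is not in the documents, so its wording cannot be checked. The unsolicited route exists, all AEs are to be documented, and with 7 group sessions and two skills sessions over 3 months there are repeated chances to mention an event. This stands as a reason not to call the list fixed. A reader might infer that ER visits and hospitalizations are under-counted as a matter of fact. The text supports only a risk, because everything off the list could be volunteered. The reply does not remove that risk: even a general Other line would leave the care question attached to an event already named.

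A reader might also infer that every hospital stay is an SAE. Section 8.3.1 requires an untoward medical occurrence, 8.3.2 requires that the event result in the admission, and 8.3.4 treats conditions present at screening as baseline unless they worsen. A planned admission for an unchanged condition need not qualify. An ER visit is not in itself an SAE criterion, so for ER visits the point rests on 9.4.4 alone.

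Finally, safety is not a study endpoint in section 3, the study is described as minimal risk, and no hypothesis or stopping rule uses these rows. That is correct and limits the importance of the point.

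**Conclusion.** The mismatch is in the text. Active ascertainment of emergency and hospital use is tied to the solicited events, off-list use relies on passive reporting without a named data item, and 9.4.4 reports both counts with no matching limit. The ER and hospitalization counts may be incomplete, and so may SAE capture for events that lead to admission.

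The conclusion assumes that the questionnaire follows 8.3.4 as printed. Any percentage would rest wholly on assumed inputs, and the documents do not establish that an under-count will occur. Because the tables are descriptive, in a pilot of about 20, no inference changes. This is a worthwhile low-cost improvement and not a flaw that threatens the trial's aims.

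**What to change.** In 8.3.4, begin each adverse-event contact with one all-cause question: since the last contact, has the participant gone to an emergency room or stayed overnight in a hospital for any reason? Record the reason, then go through the existing list. Name emergency and hospital use as a data item for every AE and SAE, solicited or not.

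In 9.4.4, state that the ER and hospitalization counts are built from that answer. Assess each reported stay against the AE definition in 8.3.1, the baseline-condition rule in 8.3.4 and the SAE criteria in 8.3.2. SAE status should not be read directly from the all-cause answer, or planned and baseline-condition stays would be misclassified.

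The cost is one more question per contact on an existing form, plus some reported stays that turn out not to be AEs. If the form cannot be changed, the minimum is a sentence in 9.4.4 saying that these counts cover solicited events and whatever else was volunteered.
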